Despite evidence that both rapid weight gain⁷ and excessive body fat accrual⁸ are associated with overweight and obesity, usual neonatal care for preterm infants does not include the assessment of body fat accrual. Similarly, screening programs to assess body composition in infants with a history of prematurity have not been established. By monitoring body fat accrual in preterm infants before and after hospital discharge, clinicians could modify dietary interventions in early infancy and prevent obesity and long-term related morbidities. In this pilot randomized trial, we will test the central hypothesis that very preterm infants (28 to 32 weeks of gestation as defined by the World Health Organization) managed using information from monthly serial assessments of infant body composition from birth to hospital discharge will have lower percent body fat (%BF) at 3 months of age than infants managed using standard care (weight and other routine growth parameters). %BF at 3 months of age has a strong correlation with %BF at 4 years of age⁹. Our long-term goal is to develop a comprehensive nutritional program that incorporates assessment of body composition in the routine care of preterm infants and reduces variability in feeding practices before and after hospital discharge to minimize the risk of obesity mediated by rapid weight gain.

Specific Aim 1: To test the hypothesis that provision of serial body fat accrual reports during hospitalization will enable personalized dietary interventions and reduce adiposity at 3 months of age in very preterm infants. We chose %BF at 3 months of age as the primary outcome of the trial because at this age: 1) body fat accrual can be measured with non-invasive methods¹⁰; 2) loss to follow-up rates are low⁹; 3) physical activity and other risk factors for obesity are less likely⁷; and 4) correlation with body fat accrual at preschool age is strong⁹. We selected very preterm infants as the ideal population to study the risk of obesity in preterm infants because they: 1) experience a high risk for adverse health outcomes^{3,5}; 2) usually do not require supplemental oxygen after postnatal day 7; and 3) receive strictly controlled diets for more than 30 days from birth to hospital discharge. With our improved understanding of the interaction between infant weight, body fat accrual, and dietary interventions, we plan to examine whether the provision of body fat accrual reports to clinicians and parents will impact infant weight gain and body fat accrual¹¹.

Specific Aim 2: To test the hypothesis that serial assessment of infant body composition attenuates health disparities in body fat accrual at 3 months of age by slowing weight gain following hospital discharge. The rationale for this aim is: 1) rapid weight gain during early infancy is highly prevalent among racial/ethnic minorities^{12,13}; and 2) adjustment for rapid weight gain attenuates disparities in childhood obesity between racial/ethnic minorities and white infants^{7,12}. We hypothesize that our intervention focused on personalized dietary interventions based on changes in infant body composition will reduce rapid weight gain and attenuate health disparities in body fat accrual.

RESEARCH STRATEGY

SIGNIFICANCE

Rapid weight gain increases the risk of metabolic reprogramming in preterm infants. For many years, the high prevalence of postnatal growth failure (weight below the 10th percentile for expected intrauterine growth) in the preterm population made weight the most important outcome of growth among preterm infants. Similarly, the association between rapid weight gain and improved neurodevelopment led clinicians to assume that slow weight gain was “inadequate growth” and that high-calorie diets to promote rapid weight gain were needed.

Available clinical evidence no longer supports these assumptions. Current dietary interventions have not appreciably reduced postnatal growth failure. Postnatal growth failure remains prevalent and occurs in approximately 60%¹⁴⁻¹⁶ of the nearly 80,000 infants born preterm at 32 weeks of gestation or less every year in the United States². Similarly, the benefits of rapid weight gain on neurodevelopment of preterm infants have not been consistently demonstrated. While 19 observational studies of low to moderate quality have associated rapid weight gain with improved neurodevelopmental outcomes¹⁷, 3 randomized trials of hospital-based nutritional interventions that reversed postnatal growth failure through rapid weight gain did not show benefits in neurodevelopment¹⁸⁻²⁰. These inconsistencies between results from randomized trials and results from low to moderate quality observational studies suggest the presence of unmeasured confounding factors that affect both growth and cognition¹⁷ and demand caution with the assumption that promoting brain development through rapid weight gain outweighs the risk of potential long-term metabolic dysfunction.

Rapid weight gain also known as catch-up growth could trigger changes in metabolic reprogramming. Results from interventional and observational studies indicate that high-calorie diets before and after hospital discharge to promote catch-up growth and prevent postnatal growth failure among preterm infants²¹ may result in hypertension, insulin resistance²², and disproportionate increase of body fat^{17,23}, particularly when carbohydrates and fat are the primary source of energy. This clinical evidence of metabolic dysfunction resulting from rapid weight gain has been demonstrated in humans and animal models. Clinical studies consistently show that growth-restricted preterm infants are more likely to experience catch-up growth^{15,24} and corroborate conclusions from animal experiments that reveal an increased susceptibility to early metabolic reprogramming of adverse health outcomes in developing infants exposed to high-calorie diets^{17,25,26}. In rats and mice with growth restriction as a result of poor maternal diet, rapid growth due to high-calorie diets increases susceptibility to obesity and reduces longevity^{27,28}. The mechanisms of early metabolic reprogramming include permanent changes in organ structure due to suboptimal nutrition, epigenetic modifications that lead to changes in gene expression, and permanent effects on regulation of cellular aging²⁵.

Assessment of infant body composition offers important advantages over BMI as outcome of growth. BMI and infant body composition are outcomes of growth associated with long-term health. BMI is a widely accepted anthropometric index that is used to define obesity, but in early infancy, BMI has poor predictive accuracy for obesity and poor correlation with body fat accrual. In term infants, BMI only explains up to 43% of the variation in fat mass (FM)^{29,30}. Furthermore, reduction of infant BMI to prevent obesity in adulthood is not currently recommended because high infant BMI values are associated with greater lean mass³¹. Body fat accrual during early infancy is a marker of fetal adaption and metabolic reprogramming that has a significant association with obesity and other adverse health outcomes³². Rapid weight gain is associated with higher risk of %BF, abnormal fat distribution, and overweight at school age^{8,33}.

Air-displacement plethysmography (PeaPod®, Life Measurement Instruments, Concord, CA) is one the less invasive and more accurate methods to assess infant body composition in early infancy^{32,34}. Using air-displacement plethysmography, several studies have determined reference values of neonatal body fat accrual at different gestational ages^{6,10}. At birth, body fat accrual expressed as %BF ranges from 6% at 30 weeks of gestation to 9.5% at 37 weeks of gestation.¹⁰ At term-equivalent age, all preterm infants have significantly higher %BF than infants born at term (up to 6% higher when measured by air-displacement plethysmography)²⁹, irrespective of history of intrauterine growth restriction³⁵.

While studies that assessed infant body composition with either dual energy X-ray absorptiometry or bioelectrical impedance analysis suggest that fat free mass (FFM) can be predicted using weight data³⁶, studies that assessed infant body composition with air-displacement plethysmography, a method with high accuracy and validity when compared to the gold standard carcass analysis³², suggest an unreliable correlation between anthropometric data and neonatal adiposity³⁷ and body composition³⁰ in preterm infants.

Body fat accrual at 3 months of age predicts infant body composition at 4 years of age. Unlike body composition at term-equivalent age, body composition at 3 months of age has a strong correlation with body composition at 4 years of age in infants born preterm⁹. Large observational studies suggest that differences in body composition between term and preterm infants persist into adulthood^{4,5}, but the implications of early alterations of growth and body composition are largely unknown despite evidence that early rapid weight gain and body fat accrual are determinants of later obesity risk in full-term and preterm infants^{5,38-40}. Taken together, these data suggest that early changes in body composition following hospital discharge could be an important outcome of growth to analyze long-term health risks of rapid weight gain and body fat accrual during early development. Serial monitoring of body composition during infancy may allow nutritional support optimization that balances neurodevelopmental benefit and metabolic risk⁹.

Slow weight gain after hospital discharge attenuates the risk of obesity among racial/ethnic minorities. Observational studies show that obesity and rapid weight gain in early infancy are more prevalent among blacks and Hispanics than among whites and that differences in feeding practices (breastfeeding rates, early introduction of complimentary foods and others) contribute to these disparities in infant weight gain and obesity^{12,13}. Adjustment for these early risk factors related to infant feeding attenuates disparities in childhood obesity between minority and white infants^{7,12}; therefore, it is plausible that, by providing more specific information about early changes in body composition instead of using an anthropometric index, clinicians and parents may alter their feeding regimens before and after hospital discharge in a manner that will reduce the risk for unhealthy gains in adiposity. Modifications of these early risk factors could have a substantial impact on preventing disparities in childhood obesity¹².

INNOVATION

Despite clinicians' ability to effectively control all external sources of nutrition in the immediate neonatal period, current dietary interventions and methods to assess postnatal growth have not led to significant improvement in growth and neurodevelopment. Comprehensive evaluation of postnatal growth with infant body composition is essential to guide appropriate and effective nutritional interventions for infants at high risk of obesity.

The incorporation of a longitudinal assessment of infant body composition into current practices of neonatal care is innovative because it will provide a more sensitive index of the infant's body habitus and thereby guide clinician decisions about dietary interventions. This change in practice could reduce the risk of overweight and obesity in very preterm infants.

Serial assessment of infant body composition using air-displacement plethysmography, a validated method with reliable accuracy, to report body fat accrual in a randomized clinical trial is also one of the novel aspects of our proposal, as other research studies have used low-accuracy methods to estimate infant body composition⁶.

APPROACH

Our central hypothesis is that very preterm infants managed using information from serial assessments of infant body composition during their initial hospitalization will have lower percent body fat (%BF) at 3 months of age, irrespective of sex and race/ethnicity.

Specific Aim 1 will test the hypothesis that, after establishing a program to monitor infant body composition before and after hospital discharge, identification of changes in body fat accrual will prompt individualized recommendations for dietary interventions that reduce %BF at 3 months of age in very preterm infants.

Overview: Aim 1 will be a pilot randomized trial in which 50 very preterm infants will be randomly assigned in a 1:1 allocation ratio to either routine neonatal care (control group) or neonatal care with serial assessments of infant body composition (intervention group). The primary outcome will be %BF at 3 months of age [Table 1].

Table 1. Project timeline

Critical steps	Month											
	Jun	Jul	Aug	Sep	Oct	Nov	Dec	Jan	Feb	Mar	Apr	May
Anticipated IRB approval (protocol & consent form)												
Patient screening and enrollment												
Body fat assessment at 3 months of age												
Primary & secondary data analyses												
Results available for manuscript preparation												

Rationale: While weight, the key element of the operational definition of postnatal growth failure, remains useful to assess nutritional status, its limitations as the only method to assess nutritional status and health risks⁴¹ should not be ignored. The assumed benefit of catch-up growth on neurodevelopment should be weighed against the possibility that catch-up growth might cause harm and increase the risk of adult-onset metabolic disease^{24,26,42}. Because infant weight gain predicts later obesity risk⁴³, central adiposity⁴⁴ and insulin resistance⁴⁵, more research is needed to define the best strategies to provide adequate nutrition with a goal of preventing growth failure without increasing health risks of public health importance. The problem of increased adiposity soon after birth and into adulthood among preterm infants suggests that assessment of body fat accrual along with weight gain could be an effective strategy to achieve the goal of ideal growth while preventing unnecessary health risk. As defining the risk for abnormal cardiovascular and metabolic outcomes in this population has become critically important⁴⁶, it is possible that early detection of atypical changes in infant body composition characterized by excessive body fat accrual could prompt changes in dietary interventions to reduce the risk of obesity, cardiovascular disease, and metabolic syndrome later in life.

Study design

Setting: The neonatal unit at UAB is one of the largest neonatal academic centers in the United States. We have admitted more than 200 very preterm infants over the past 2 years. This large numbers of very preterm infants admitted makes our unit the ideal environment to conduct comparative effectiveness trials.

Participants: Very preterm infants with gestational ages between 28 and 32 weeks of gestation at the time of admission to our neonatal unit will be eligible for this trial. Gastrointestinal or neurologic malformations, and terminal illness requiring limited or withheld support will be exclusion criteria.

[figure not shown]
Randomization, allocation concealment, and masking: After receiving approval by the Institutional Review Board (IRB) at UAB to conduct this trial, research nurses and investigators will obtain written parental consent before randomization. We will randomize study participants using computer generated random-block sequences and numbered, opaque, sealed envelopes that will be opened in sequential order. Twin infants will be randomized individually. The intervention will not be masked.

Intervention: Infants randomly assigned to the intervention group will have the information about infant body composition known to the clinicians caring for them (including reference data). The use of this patient-specific information about nutritional status will assist clinicians to optimize nutrition using feeding guidelines that will be provided. Infants randomly assigned to the control group will also undergo serial measurements of body composition, but this information will not be available to the clinicians.

Primary and secondary outcomes: The primary outcome will be %BF estimated by air displacement plethysmography at 3 months of age. Secondary outcomes will include %BF and fat-free mass (FFM) at 36 weeks of postmenstrual age (PMA) or hospital discharge (whichever occurs first), postnatal growth restriction (below 10th percentile) at 36 weeks PMA or discharge, weight gain (g/kg/d) from birth to the end of the intervention, anthropometric measures at time of hospital discharge (weight, head circumference, and length), weight gain (g/kg/d) from hospital discharge to 3 months of age, anthropometric measures at 3 months of age (weight, head circumference, and length), and blood pressure values at 3 months of age.

Assessment of infant body composition: Serial assessments of infant body composition with air displacement plethysmography in very preterm infants using the PeaPod® (Life Measurement Instruments, Concord, CA)³² will occur in the first 14 days after birth (baseline measure), at 32 weeks PMA, at 36 weeks PMA or hospital discharge (whichever occurs first), and at 3 months of age [Figure 2]. The PeaPod® and the neonatal unit are located in the same building. During hospitalization, nursery staff and parents, if present, will transport the infant to the exam room where the PeaPod® is located. In the exam room, nursery staff will undress the infant, place the snug cap, and transfer the infant to the PeaPod® when ready for weighing and scanning. The infant will wear only a cap on his/her head and will lie inside the scanner for approximately 2-3 minutes to estimate total fat and fat-free mass according to body weight and volume⁴⁷. The infant will breathe the normal air in the room and will be able to see and hear his/her parents. Equipment for respiratory support or monitoring will not be used during the assessment to avoid unnecessary recalibration of the PeaPod®. For assessment of body composition at 3 months of age, a follow-up visit will be scheduled prior to discharge from the hospital. The 3-month visit will also include a brief questionnaire about feeding practices at home and blood pressure measurements. The study coordinator will mail a reminder letter approximately 2 weeks prior to the date of the visit and will call the caregiver to remind them on the day prior to their scheduled appointment. Infants and a caregiver will return to the hospital to repeat the body composition assessment. A trained technician from the Nutrition Obesity Research Center (which owns and manages the PeaPod®) will operate it.

Figure 2. Serial assessment of body fat accrual in very preterm infants*

* Traditional growth chart report (A) and body fat accrual report (B) of a preterm infant born at 29 weeks of gestation and monitored from birth to 36 weeks PMA

Control or monitoring of co-interventions: Clinical care and decisions about enteral nutrition will be conducted at the discretion of the attending physician.

Study specimens. Because several experiments suggest that changes in gut microbiota can influence obesity⁴⁸, we will obtain written informed consent from the parent(s) to collect 2 stool samples, 1 stool sample before hospital discharge and 1 stool sample at the 3-month follow-up visit for possible use in future studies. Similarly, consent from the parent(s) will be obtained to collect a serum sample and measure biomarkers of anabolism and growth prior to hospital discharge.

Statistical Analysis Plan. This trial will record core data on nutrition as recommended by consensus groups⁴⁹. For analysis of the primary outcome, an unadjusted T-test comparison of the mean %BF between control and intervention groups will be performed assuming a normal distribution of this variable⁵⁰. In consideration of relevant biological variables, a pre-specified adjusted analysis for demographic and nutritional characteristics will be conducted to improve precision in treatment comparisons and remove variability associated with these covariates^{51,52}. A similar approach will be used for secondary outcomes. Descriptive data will be expressed as the mean (SD) or number (percentage) of observations. The primary statistical analyses will be performed on an intention-to-treat basis⁴⁹ with SAS software.

Sample Size and Power Estimates. At our institution, the mean and SD of %BF in preterm infants at time of discharge is 15 and 3.6, respectively (unpublished data). Therefore, to detect a 3-point difference in %BF between groups with SD of 3.6, 0.05 level of significance, and 80% power for a T-test that compares means from two independent samples, a sample size of 46 patients will be necessary in this superiority trial. Anticipating that approximately 10% of study participants will be lost to follow-up for assessment of the primary outcome at 3 months of age, 2 patients will be added to each group and the sample size will be increased to 50. We will include a total of 25 patients in each group (n=50).

Potential Problems

Enrollment rates: An average of 7 study participants per month were enrolled in a recently completed trial that assessed body composition of very preterm infants at our institution (unpublished data). To define a timeline for patient enrollment in this trial, we assumed that 50% of parents will refuse participation.

Sample size: A negative outcome (i.e. %BF) was selected as the primary efficacy end point of this trial. We used our own institutional data to calculate the sample size for this trial and estimated that a 3% absolute difference was clinically meaningful because the average difference between term and preterm infants is 3%.⁶

Follow-up: We estimated that follow-up rates at 3 months of age will be higher than our follow-up rates at 2 years of age for extremely preterm infants (approximately 80% at our institution). Follow-up at 3 months of age to assess infant body composition will allow comparison of our results with reference data in term infants.

Generalizability: Given the pilot nature of this trial, we will focus on minimizing systematic errors in the trial to improve accuracy of our results and increase internal validity. It is expected that the precision of our estimates and the external validity of our results will be affected by our small sample size.

Specific Aim 2 will test the hypothesis that serial assessment of infant body composition slows weight gain following hospital discharge and attenuates health disparities in body fat accrual at 3 months of age.

Overview and preliminary data: Aim 2 will be a secondary analysis of our pilot randomized trial. In a prospective study of body composition, we corroborated that racial/ethnic minorities have higher in-hospital growth rates than white infants (unpublished data).

Inclusion criteria, exclusion criteria, and outcome: Demographic and nutritional data from infants who participated in the pilot trial will be used for this analysis. Infants with missing follow-up data will be excluded. %BF at 3 months of age will be the dependent variable in the primary analysis.

Statistical analysis: In this analysis, race/ethnicity will be entered as a dichotomous variable: white (reference group) and black or Hispanic. To examine the association between weight gain at 2 different time points (before and after hospital discharge) and body fat accrual at 3 months of age within each racial/ethnic group, we will use multivariable regression models. Subsequently, to quantify the degree to which weight gain explains racial/ethnic disparities in body fat accrual, we will employ a decomposition analysis which will help us determine if changes in weight gain after serial monitoring of body fat accrual reduces differences (i.e. observed and predicted) in body fat accrual between minority and white infants⁷.

HUMAN SUBJECTS

RISKS TO HUMAN SUBJECTS

Human Subjects' Involvement, Characteristics, and Design. This is non-exempt human subjects research.

Characteristics of participants: Our study population will reflect the epidemiology of prematurity in the state of Alabama, with approximately 56% being Black (African-American), 41% White (Non-Hispanic Caucasian), and the remaining 4% Hispanic/Other. This study population has been selected based on the frequency of nutritional problems observed at these gestational ages and the increased risk of adverse health outcomes in this vulnerable population.

Sampling plan, recruitment, and retention. Patients admitted to the neonatal unit of UAB from June 2018 to January 2019 will be screened to determine eligibility for the study. Because the protocol is designed to establish a new hospital-based practice early in life, mothers will be approached by the research staff before eligible very preterm infants reach full enteral feeding.

Sources of Materials

For study participants, data will be collected from electronic medical records. Data containing identifying information will be available only to the PI ([name]) and research personnel directly involved with this study. Information about the study will be shared without individual identifiers. Data will be collected from medical records in accordance with the study protocol. This will include demographic data and other nutrition/feeding data.

Potential Risks

Potential risks: The probability of risk for higher %BF in a patient that participates in this trial is not different than the probability of higher %BF in a patient that does not participate in the trial⁵³. Other theoretical risks of this study are related to clinical decompensation during assessment of infant body composition. They include increased risk of bradycardia or desaturations. Previous studies, including ours (unpublished data), have not reported an association between assessment of infant body composition and any of the above-mentioned risks. Infants may experience some transient discomfort during the PeaPod® assessment which requires them to wear a tight-fitting cap but no other clothing or blanket. Therefore, there are no known risks associated with this trial except loss of confidentiality, as it involves data collection.

Breach of confidentiality: The main potential risk of this study is breach of confidentiality. This is one of the most common risks of participation in clinical research. Accordingly, our team has designed a strategy to protect participant confidentiality. All participants will be informed of study procedures and gauged for understanding of study tasks. In addition, study personnel will follow regulatory guidelines for obtaining informed consent.

Alternative treatments and procedures: Participants in the intervention and control groups will have full access to all available standard of care clinical services at our neonatal unit, and parents are permitted to withdraw or refuse participation at any time.

Adequacy of Protection against Risks

Recruitment and Informed Consent

Recruitment: When a potential participant is identified, a member of the study will see the parents and/or mother in her room or the baby's room and explain the study. The risks and benefits will be discussed with the parents and time will be given to them to ask questions. It will be made known to them that no treatment will be withheld from their child if they participate in the study.

Informed consent: The research team will attempt to obtain written consent after giving the parents a minimum of 24 hours to think about the study information and ask questions. Randomization will define study group assignment

Study Monitoring Plan. This protocol will be reviewed by the IRB at UAB. Serious adverse events including severe clinical deterioration after assessment of infant body composition will be reported to the principal investigator. Moderate to major complications, defined for the purpose of this trial as events requiring immediate medical attention and/or interventions due to worsening clinical status, will also trigger a notification to the principal investigator. In previous studies that assessed infant body composition in stable preterm

infants, including ours (unpublished data), serious adverse events including bradycardia, desaturations, hypothermia, sepsis, or death were not reported. No interim analyses are planned.

Protections against Risk. Our team will make every effort to protect all participants' confidential and private information in order to minimize possible study-associated risks. All findings related to any research will be available and provided to study participants in accordance with standard practices. We will also inform all participants that their participation is voluntary, and we will utilize study identification codes in place of personal identifiers on study materials. We will also employ storage and encryption techniques in compliance with UAB Data Security standards to safeguard all electronic data, as well as protections outlined in Subpart C of title 45, part 4 Code of Federal Regulations. All study personnel are required to renew Human Subjects training biannually. No data will be accepted from or distributed to the principal investigator or study staff if regulatory training is not current.

Any provider or caregiver involved in the trial will be able to write to the study coordinator to draw attention to any concern they may have about the possibility of harm arising from the intervention under investigation.

Potential Benefits of the Proposed Research to Human Subjects and Others

Potential benefits of this study are to provide stronger evidence for the safety and efficacy of monitoring body fat accrual as a way of optimizing caloric intake, growth, and fat-free mass in preterm infants. Better quantitative and qualitative outcomes of growth may also be associated with improved long-term neurodevelopmental outcomes.

The potential benefits of this research may include reduction of postnatal growth restriction, reduction in infant morbidity mediated through improved neonatal nutrition, and better growth at time of discharge. Reductions of postnatal growth restriction and improved nutritional parameters could improve long-term neurodevelopmental outcomes of infants. There will be benefit to the medical community in providing additional information on infant body composition in preterm infants.

Importance of the Knowledge to be Gained

As the risk to individual participants is small and potential benefits are significant, the risk/benefit ratio is favorable.

ClinicalTrials.gov Requirements

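### The primary comparison adjusts for gestational age neither by stratification nor in the model, which leaves some avoidable variance; a minor point, and not a bias

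*Combined protocol and SAP*

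**What the plan says.** Under Randomization, allocation concealment, and masking, the combined protocol and SAP allocates infants by "computer generated random-block sequences and numbered, opaque, sealed envelopes", with the envelopes taken in number order. No stratification factor is named there. The study figure near that text is not reproduced in the copy reviewed, so the absence of strata rests on the written method.

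Under Participants, eligible infants have "gestational ages between 28 and 32 weeks of gestation at the time of admission".

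The Statistical Analysis Plan paragraph states, for the primary outcome, that "an unadjusted T-test comparison of the mean %BF between control and intervention groups will be performed". It then adds "a pre-specified adjusted analysis for demographic and nutritional characteristics will be conducted to improve precision in treatment comparisons". That second analysis gives its covariates by class only. Gestational age is not named, and nothing makes this analysis the primary one.

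The one figure relating %BF to gestational age is in the Significance section and refers to birth: "body fat accrual expressed as %BF ranges from 6% at 30 weeks of gestation to 9.5% at 37 weeks of gestation".

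**The concern.** Blocking balances the number of infants per arm, not their maturity. With 25 infants per arm and a five-week eligibility range, the arms can differ by chance in mean gestational age, and an unadjusted t-test does nothing about it. If gestational age predicts %BF at 3 months, its contribution stays in the error term and the single realised estimate carries whatever imbalance occurred.

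Two features make a relation plausible. %BF at birth varies with gestational age on the plan's own figures. Also, the documents do not say whether 3 months of age is chronological or corrected. If it is chronological, infants born at 28 and at 32 weeks are measured about 4 weeks of postmenstrual age apart.

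At stake is some power in a trial that has little to spare, and how readable its one estimate will be.

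**Working it through.** **Inputs.** From Sample Size and Power Estimates: difference 3 points, SD 3.6, alpha 0.05, power 80%, 50 enrolled, about 10% lost. From Significance: %BF at birth 6% at 30 weeks and 9.5% at 37 weeks. Assumed, because not given: births uniform over 28w0d to 32w6d, and the slope b of 3-month %BF on gestational age.

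**The plan's sample size.** n per arm = 2 × (1.96 + 0.842)² × 3.6² / 3² = 22.6, rounded up to 23, or 46 in total. This matches the plan. The sample-size figure is not in question here.

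**Evaluable infants.** 50 × 0.90 / 2 = 22.5 per arm. Standard error of the difference = 3.6 × √(2/22.5) = 1.073. Noncentrality = 3 / 1.073 = 2.795 on 43 degrees of freedom. Power of the unadjusted t-test = 78.0%.

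**Chance imbalance.** SD of gestational age = 5/√12 = 1.44 weeks. With 25 per arm, the standard error of the difference in means = 1.44 × √(2/25) = 0.41 weeks. The chance of a difference above half a week is 22%. If the SD were 1.0 week, the standard error would be 0.28 weeks and the chance 8%.

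**Slopes.** The only documented slope is (9.5 − 6)/(37 − 30) = 0.5 points per week, at birth. I take 0, 0.5 and 1.0. Sign does not matter, because the gain depends on b².

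**Effect on the comparison.** Chance shift (95%) = 1.96 × b × 0.408. R² = (b × 1.443)² / 3.6². Adjusted SD = 3.6 × √(1 − R²). Adjusted power uses 42 degrees of freedom. The last column also allows for the expected chance correlation between arm and covariate, which multiplies the variance by about 1 + 1/(45 − 4) = 1.024.

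| Slope (points/week) | R² | Adjusted SD | 95% chance shift, unadjusted | Power, unadjusted | Power, adjusted (degree of freedom only) | Power, adjusted (with the 1.024 factor) |
|---|---|---|---|---|---|---|
| 0 | 0 | 3.60 | 0 | 78.0% | 78.0% | 77.0% |
| 0.5 | 4.0% | 3.53 | ±0.4 | 78.0% | 79.6% | 78.6% |
| 1.0 | 16.1% | 3.30 | ±0.8 | 78.0% | 84.6% | 83.8% |

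With the 1.024 factor, adjustment breaks even at R² = 1 − 1/1.024 = 2.4%, which is b = 3.6 × √0.024 / 1.443, or about 0.4 points per week.

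**Sensitivity to the spread of gestational age.** With an SD of 1.0 week, R² falls to 0.5²/3.6² = 1.9% and 1.0²/3.6² = 7.7%. The 95% shifts are ±0.3 and ±0.6 points, and adjusted power (degree of freedom only) is 78.7% and 81.1%.

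**Simulation check.** 40,000 trials per slope, 23 per arm, gestational-age SD 1.41 weeks. At 0.5 points per week, power was 78.9% unadjusted and 79.5% adjusted; at 1.0 it was 78.6% and 84.2%. Type I error was about 5% for both analyses.

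**The case against.** The strongest reply has four parts.

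1. *The plan already adjusts.* It does pre-specify an adjusted analysis, with improved precision as its stated purpose, so it would be wrong to say that it ignores covariates. But that analysis supplements the t-test and does not name gestational age. The objection softens the point without removing it.

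2. *The slope is unknown.* This stands. The 0.5 figure is a cross-section at birth, not at 3 months. The same section says that preterm infants at term-equivalent age have higher %BF than term-born infants, so even the direction at 3 months is open. Zero is possible, and there adjustment gains nothing.

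3. *The effect is small at the documented slope.* This also stands: a gain of 1 to 2 power points on the degree-of-freedom calculation, or under 1 with the correlation allowance. A reader might reach a much larger effect by joining 6% at 30 weeks to the institutional mean of 15% at discharge, or about 1.5 points per week if discharge is near 36 weeks. The documents do not support that as a gestational-age slope. It is fat gain over postnatal time, joined from two different sources.

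4. *Validity is not affected.* Correct. A reader might infer that unstratified blocks with an unadjusted test bias the result or inflate false positives. Randomisation protects against that, and the simulation agrees. The longer in-hospital period of the least mature infants is a matter of possible effect modification, not of bias through imbalance.

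**Conclusion.** The point holds as a minor improvement in efficiency. Neither the allocation nor the primary test uses gestational age, and the one analysis that might is secondary and leaves it unnamed. Under uniform births and 22.5 evaluable infants per arm, adjustment is roughly neutral at zero slope (a loss of up to about 1 power point), gains about 0.6 to 1.6 points at 0.5 points per week, and gains about 6 to 7 points at an assumed 1.0. A narrower spread of gestational age makes all of these smaller.

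The documents do not support a finding that the primary test is invalid, that imbalance is likely to imitate much of the 3-point target, or that stratified randomisation is required. The case for change is the lopsided trade: a small loss if gestational age is unrelated to the outcome, and a larger gain if it is moderately related. The Generalizability paragraph itself expects precision to suffer from the small sample.

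**What to change.** In the Statistical Analysis Plan paragraph, define the primary comparison as a linear model of 3-month %BF on arm plus gestational age at birth, entered as a continuous covariate. Keep the unadjusted t-test as a supporting analysis. Fix this before any outcome comparison by arm is made.

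Gestational age is an eligibility criterion, so no new data are needed. The cost is one degree of freedom, which is under 0.1 power point at zero slope. Chance correlation between arm and gestational age adds about 1 further point of cost in that case.

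Stratified envelope series are optional and not required. On the same assumptions, counting degrees of freedom only, a two-level stratum in the model gives 79.1% and 82.7% power at slopes of 0.5 and 1.0, against 79.6% and 84.6% with continuous gestational age. The covariate therefore does at least as well without changing the allocation procedure.
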